BRIEF ADMISSION BY SELF-REFERRAL FOR INDIVIDUALS WITH SELF-HARM.

Effects on compulsory care.

Official title: Brief Admission by self-referral for individuals with self-harm. Effects on compulsory care.

NCT number: 2022-02307-01

Date: 2024-04-24

BRIEF ADMISSION BY SELF-REFERRAL FOR INDIVIDUALS WITH SELF-HARM.

Effects on compulsory care.

STUDY PROTOCOL

AIM AND RESEARCH QUESTIONS

The overarching aim of this project is to evaluate the effect of Brief Admission by self-referral (BA) added to treatment as usual, on compulsory care in adults.

Primary research question:

1. Does implementation of BA decrease the number of days with compulsory admissions, in individuals with repeated self-harm and traits of borderline personality disorder (BPD)?

Secondary research questions. In individuals with repeated self-harm and traits of BPD:

2. Does implementation of BA decrease the number of compulsory admissions?
3. Does implementation of BA decrease the number of compulsory acts?
4. Does implementation of BA affect the number of voluntary psychiatric admissions?
5. Does implementation of BA affect the number of days with voluntary psychiatric admissions?
6. Does implementation of BA affect the duration of free intervals between admissions?
7. Does implementation of BA affect mortality?

AREA OVERVIEW

Self-harm is common in psychiatric care, about three out of four adolescents and half of the adults report having self-harmed in the past six months (1). For individuals with repeated self-harm and traits of BPD, consensus on the management of imminent suicidality is still lacking. For this group, admission to inpatient care can on one hand be lifesaving, but on the other hand have severe iatrogenic effects such as aggravated self-harm and prolonged compulsory admissions (2,3). For this purpose, Brief Admission by self-referral (BA) has evolved providing patient-controlled health care aiming to reduce self-harm and compulsory care and promote autonomy in a person-centered approach (4). Although this method is relatively new in Sweden, it has been used in the Netherlands for the last 30 years with positive experiences (5).

Brief Admission by self-referral (BA) is a crisis-management strategy, welcomed as a promising intervention for a variety of psychiatric disorders, standardized for persons with repeated self-harm and traits of BPD (4,6). The characteristics of BA are profoundly different from other psychiatric hospital admissions since BA promotes autonomy by entailing self-admission and removing gatekeeping mechanisms (4,7). BA represents a shift in Swedish psychiatric care from a model that generally protects people from harming themselves through exercise of control, to one that promotes autonomy.

With admissions limited to a maximum of three nights, three times per month, BA is made available to targeted individuals after the negotiation of a contract, that explains the

BRIEF ADMISSION BY SELF-REFERRAL FOR INDIVIDUALS WITH SELF-HARM.

Effects on compulsory care.

intervention and settles individual details. The contract specifies services included (e.g. conversations with staff) and excluded (e.g. changes in medication, consultation with a ward physician). Furthermore, the contract contains individualized components such as goals and strategies as well as a person's commitments during BA, such as to bring and administer their medication (4). In addition, the person admitted to BA agrees not to harm themselves or others and to take on the overall responsibility for their own security. If a person is unable to maintain these commitments during BA, they are discharged from the current BA but can seek the psychiatric emergency unit or admit themselves to a new BA the following day. BA is handled by nurses, or if nurses are not available, nurses' aides, whose clinical approach is to be welcoming with warmth, enthusiasm, acceptance, genuineness, openness, validation, and a willingness to collaborate on equal terms (4). To ensure efficient targeting, BA is provided as an integrated part of general psychiatric care after an assessment by the outpatient team together with the BA unit. Thus, a self-admission as per the BA method will be aligned with the individual and their team's long-term idea of optimal treatment for that individual. BA is followed up and evaluated regularly with contract renewal and revisions to ensure adaptation to current needs.

Brief self-referral initiatives focused on increasing autonomy and self-esteem while reducing voluntary and compulsory admission to psychiatric care, have evolved in several countries (6). In Sweden, BA has been well received among health care providers (8) and persons using it (9). Individuals with severe self-harm and a history of extensive compulsory and voluntary psychiatric admissions describe their experience with BA as a worthy respite, replacing the conventional system where the need for admission must be proved 'in blood' or where one must wait until symptoms worsen (10). BA has been enthusiastically embraced as refreshing and novel by staff, avid for a new approach for the demanding care of persons with extensive self-harm and suicidal behavior. BA offers structure and a balance of requiring responsibility of the individual, while being able to welcome persons during times of approaching crisis. Staff providing BA for this group emphasize the benefits of predictability of the admissions, e.g. neither the length of the admission nor the responsibility of the individual can be negotiated. Furthermore, they described a shift from trigger and conflict to collaboration with the individual at the ward, as well as an increased alignment between inpatient and outpatient caregiving (11). Also, the intervention is experienced as safe, even provided to a group with prolonged and imminent suicidality, who are made responsible for their own safety.

The initial reports of a striking decrease of compulsory and voluntary admissions alongside increased use and implementation of self-referral initiatives (6) are hampered by the lack of control groups. Two randomized controlled studies that did not reproduce this decrease, lack measures for treatment fidelity (12,13). The Brief Admission Skåne Randomized Clinical Trial (BASRCT) was implemented in accordance with best practice for enhancing treatment fidelity in health behavior change studies (7). The sample studied in BASRCT consisted of individuals with self-harm and three or more traits of BPD. Participants were randomized to 1) the BA group that was offered BA and treatment as usual or 2) the control group that received treatment as usual. Participants were followed for 12 months. Both the BA and control group demonstrated a similar significant within-group decrease in the number of days admitted to the hospital. However, in the BA group there was a significant within-group decrease in the number of days with compulsory admission to hospital, as well as in non-

BRIEF ADMISSION BY SELF-REFERRAL FOR INDIVIDUALS WITH SELF-HARM.

Effects on compulsory care.

suicidal self-injuries (NSSI), indicating a possible positive effect in terms of reducing iatrogenic effects related to admissions for this group (2, 3). Furthermore, in the BA group, about twenty percent of the total number of days in hospital consisted of BA, implying that BA may partly substitute voluntary or compulsory admission to psychiatric care. Among secondary outcomes, the BA group showed greater improvement as compared to controls in the domain of mobility as part of daily life functioning, meaning moving inside and outside of the home environment. Furthermore, the BA group, but not the control group, showed within-group improvement regarding cognition, domestic responsibilities, and participation in daily life after BA enrollment, as compared to before.

The major difficulty in evaluating BA is preventing the control group from cross-contamination (7). In the implementation process of BA, according to the BASRCT manual, all physicians, all inpatient and outpatient staff as well as managers need to be informed and undergo basic education regarding the intervention (4). As BA addresses a prevalent and frustrating issue in psychiatric health care, there is considerable risk that the approach leaks to the control group, reducing the possibility to detect between-group differences. For example, staff have shared experiences of a change in the workplace alongside their work with BASRCT, related to a development of more positive attitudes towards all patients at the inpatient unit (11). Indeed, in BASRCT both the BA and control group demonstrated a significant within-group decrease in general psychiatric admissions.

In this project we aim to address these methodological difficulties in exploring the effects of BA, by making use of the richness of existing data in the Swedish regional and national registers (7). We will evaluate effects of implementing BA within sites, comparing data from before and after implementation. We will also compare equivalent sites which have implemented BA at different timepoints, using relevant clinical data from registers.

PROJECT DESCRIPTION

METHODS

Research questions will be evaluated through registers, i.e. no new data will be collected from individual participants. A cohort will be created including all individuals fulfilling inclusion criteria. There are two cities where the standardized version of BA is fully implemented, with a separate ward for BA (Lund and Helsingborg). Two equivalent cities of similar size and distribution, implementing the same standardized version at a later timepoint, were found (Linköping and Norrköping). In Lund, BA was implemented in 2015, as compared to 2021 in Linköping. In Helsingborg, BA was implemented in 2017, compared to 2021 in Norrköping. Retrospective data from 2010-2022 as well as prospective data, from the date of inclusion until 2025-12-31, death or moving out of the uptake area, will be used.

The target group of this project are individuals with repeated self-harm and traits of BPD. As psychiatrists from all sites are members of the research team, different diagnostic traditions between sites have been revealed. To best detect the target group, inclusion criteria not only involves BPD but also other conditions with partly overlapping traits and which in the presence of self-harm and hospitalization can be extremely difficult to distinguish from BPD.

BRIEF ADMISSION BY SELF-REFERRAL FOR INDIVIDUALS WITH SELF-HARM.

Effects on compulsory care.

PARTICIPANTS

Participants will be identified from regional health care registers for the counties of Skåne and Östergötland and the National Patient Registry, containing all compulsory care since 2010. Data will be crosslinked using participants' Swedish national identity numbers. National register data will be de-identified prior to data analysis.

Inclusion criteria:

- Living in the uptake area of Lund, Linköping, Helsingborg or Norrköping
- Age: persons aged 18-65 years at the time of inclusion
- Admitted to hospital either diagnosed according to International Classification of Diseases, Tenth Revision (ICD-10) with BPD (F60.3, or admitted at least twice with Intentional self-harm X60-83 in combination with one of more of the following diagnoses Attention deficit hyperactivity disorder (ADHD, F90.0-F90.X), Bipolar disorder type 2, (F31.8W, F318A-F, F31.0, F31.8-9, F31.8W) or Autism, Atypical autism, Aspergers syndrome (F84.0, F84.1, F84.5) or Mild intellectual disability (F70.0-F70.9).

OUTCOME MEASURES AND COMPARISONS

Primary outcome measure:

- Days with compulsory admission (days/year)

Secondary outcome measures:

- Voluntary psychiatric admission (days/year)
- Admissions with BA (days/year)
- Compulsory admission – median length (days/admission)
- Voluntary psychiatric admissions – median length (days/admission)
- Number of compulsory admissions (admissions/year)
- Number of BA admissions (admissions/year)
- Number of voluntary psychiatric admissions (admissions/year)
- Duration of free intervals between admissions (days)
- Differences in distribution of diagnoses between men and women

BRIEF ADMISSION BY SELF-REFERRAL FOR INDIVIDUALS WITH SELF-HARM.

Effects on compulsory care.

- Mortality

REGISTERS, VARIABLES RETRIEVED, MOTIVATION

Regional healthcare data bases

- Dates for seeking care, Diagnoses, Age, Gender.
- Motivation: Inclusion criteria, secondary outcome measures

National Patient Register

- Data on compulsory care (admissions and compulsory acts), Diagnoses, Age, Gender
- Motivation: primary and secondary outcome measures

National Cause of Death Register

- Cause of death
- Motivation: secondary outcome measure

The Total Population Register

- Gender, Marital status, Country of birth, Spouse or registered partner, Cohabitation, Date of death.
- Motivation: To secure that included individuals live in the uptake areas and to adjust for potential confounding factors/effect modifiers.

National Prescribed Drug Register

- Drugs retrieved from the pharmacy: Number of packages, Anatomical Therapeutic Chemical code (ATC-code), date of expiry, corresponding daily dose
- Motivation: Certain medical conditions are well captured by prescribed drugs. This is informative with regard to confounding factors/effect modifiers.

Longitudinal Integrated Database for Health Insurance and Labour Market Studies

- Income, means of subsistence, number of persons in the household
- Motivation: Obtaining information on confounding factors/ effect modifiers that we need to adjust for alternatively make separate subgroup analyses.

STATISTICAL ANALYSES PLAN

The following comparisons will be performed:

BRIEF ADMISSION BY SELF-REFERRAL FOR INDIVIDUALS WITH SELF-HARM.

Effects on compulsory care.

- Within sites, before and after introduction of BA.
- Pairwise, between equivalent sites, before BA was introduced.
- Pairwise, between equivalent sites, after BA was introduced at one of them.
- Pairwise, between equivalent sites, after BA was introduced at both.
- Between men and women, adjusted for age and diagnoses.

Overall, the studies will have good statistical power, which can be illustrated with the following example. If we assume that about 50% of the individuals receiving treatment as usual had at least one admission that was >7 days, and with 80% statistical power we want to find a significant decrease (i.e. $p<0.05$) to 25% when BA was introduced, then 66 individuals have to be included in each group. In Lund about 40 patients are recruited each year, which means that we will have at least 200 patients in each group in a five-year period. Preliminary data indicates that halving the number of days with compulsory admission is a reasonable assumption, and in addition it is also of clinical significance.

SIGNIFICANCE

The proposed study will fill important knowledge gaps addressing potential implications of BA for compulsory care, which appears to have decreased substantially at clinics where BA has been implemented, according to preliminary data. A longitudinal register-based study, following a cohort in sites where BA is fully implemented and comparing it to a cohort in equivalent sites where BA is implemented at a later timepoint, will avoid potential contamination of educating all staff on the intervention. It will also enable correction for effects of other trends in health care during the last decade, e.g. those introduced by national initiatives such as the Swedish National Self-Injury Project (14) and *Bättre vård, mindre tvång* (“Better care, less coercion”; 15). Such a study will add to previous research and will, to the best of our knowledge, be the first of its kind.

PRELIMINARY AND PREVIOUS RESULTS

Our research group evaluated BA in a randomized clinical trial among persons with self-harm and traits of BPD in four adult psychiatric clinics in Skåne (7). We found that both the group with access to BA and the control group showed significant decreases in days admitted to the hospital and in visits to the emergency department, but only the BA group showed a significant decrease in duration of compulsory admissions and frequency of NSSI. No significant between-group differences were found in these variables. We also found an increase in several dimensions of daily life functioning in the BA group, that were not found in the control group. Furthermore, we have explored the lived experiences of individuals with life-threatening self-harm behavior and previous extensive experience of hospital admissions (compulsory and voluntary), as well as the experiences of the staff caring for them (10, 11).

BRIEF ADMISSION BY SELF-REFERRAL FOR INDIVIDUALS WITH SELF-HARM.

Effects on compulsory care.

For these individuals, BA was described as a safe and worthy respite, without triggers aggravating self-harm, which may lead to compulsory admissions.

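### The cohort is not restricted to people with repeated self-harm, its two entry routes set unequal thresholds, and the site comparisons name no adjustment for route

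*Combined protocol and SAP*

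**What the plan says.** METHODS states: "The target group of this project are individuals with repeated self-harm and traits of BPD". The primary research question under AIM AND RESEARCH QUESTIONS names the same population.

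The diagnostic criterion under PARTICIPANTS is an either/or:

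- Route A: "Admitted to hospital either diagnosed according to International Classification of Diseases, Tenth Revision (ICD-10) with BPD (F60.3, or"
- Route B: "admitted at least twice with Intentional self-harm X60-83", together with at least one diagnosis from a list: ADHD, bipolar type 2, autism spectrum conditions and mild intellectual disability.

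No exclusion criteria are given, and self-harm is not required anywhere else.

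METHODS explains why route B exists. Among the site psychiatrists, "different diagnostic traditions between sites have been revealed", and for that reason "inclusion criteria not only involves BPD but also other conditions with partly overlapping traits".

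STATISTICAL ANALYSES PLAN lists within-site comparisons before and after BA and three pairwise site comparisons, including "Pairwise, between equivalent sites, after BA was introduced at one of them". None of these names an adjustment. The comparison of men and women is the only one listed with adjustment for diagnosis.

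**The concern.** Two things follow from the unequal thresholds.

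First, the criteria do not ensure the population named in the research question. A person admitted once with F60.3 and never coded for self-harm is in the cohort, so a conclusion about repeated self-harm would rest partly on people who were not required to have it.

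Second, the threshold depends on the diagnosis the local clinic prefers. The same patient can qualify at a first admission where BPD is coded, but only at a second self-harm admission where another listed diagnosis is used. If the sites in a pair differ in this habit, their cohorts differ in severity and in the point in the illness at which people enter. An unadjusted site comparison then mixes case mix with the effect of BA. A change in F60.3 coding over time would do the same to the before/after comparison.

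**Working it through.** **1. The two routes side by side** (from PARTICIPANTS)

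| Patient | Qualifies? | Earliest point |
|---|---|---|
| F60.3, one admission, no X60-83 | Yes | That admission |
| ADHD, one X60-83 admission | No | – |
| Two X60-83 admissions, coded F60.3 from the first | Yes | First admission |
| Two X60-83 admissions, coded ADHD | Yes | Second X60-83 admission |

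The last two rows can be the same clinical picture under two coding habits. The bracket after F60.3 is not closed in the text, but the either/or wording makes two routes the natural reading.

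**2. The plan's own sample size** (STATISTICAL ANALYSES PLAN: 50% v 25% with an admission longer than 7 days, 80% power, p<0.05; two-sided testing assumed)

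- Uncorrected: n = [1.96·√(2·0.375·0.625) + 0.8416·√(0.5·0.5 + 0.25·0.75)]² / 0.25² = 57.7
- Continuity-corrected: n = (57.7/4)·[1 + √(1 + 4/(57.7·0.25))]² = 65.4, so 66 per group, as stated.

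The plan expects at least 200 per group. Power there for 50% v 25% is above 99%.

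**3. Case mix with no BA effect** (shares and rates are assumptions, applied to the plan's binary example rather than to days per year)

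Site rate = s·p_low + (1 − s)·p_high, where s is the share of low-severity entrants.

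- s = 20%: 0.2·20% + 0.8·50% = 44%
- s = 40%: 0.4·20% + 0.6·50% = 38%
- Spurious difference: 6 points
- At 200 per site, pooled SE = √(2·0.41·0.59/200) = 0.0492 and unpooled SE = 0.0491. The chance of significance in that direction is Φ[(0.06 − 1.96·0.0492)/0.0491] = Φ(−0.74), about 23%.

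Range over assumed (p_low, p_high) of (20%, 50%), (30%, 60%) and (10%, 50%):

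| Low-severity shares | Spurious difference | Declared significant |
|---|---|---|
| 20% v 40% | 6–8 points | 22–38% |
| 20% v 60% | 12–16 points | 67–93% |

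**4. Dilution of a real effect** (also assumed)

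People without repeated self-harm are a share s of the cohort, with rate p_low of 10–30% and no effect. The others go from 50% to 25%. The control rate is (1 − s)·50% + s·p_low, and the BA rate is (1 − s)·25% + s·p_low. The n is continuity-corrected; power is uncorrected.

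| s | n per group | Power at 200 |
|---|---|---|
| 20% | 94–99 | about 99% |
| 40% | 148–170 | 89–93% |
| 60% | 279–366 | 57–69% |

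If the unaffected people instead have the full 50% rate, n is 103 at s = 20% (50% v 30%) and 183 at s = 40% (50% v 35%). Both are below 200.

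**The case against.** **The asymmetry has a stated reason.** F60.3 is direct evidence of BPD, while ADHD or autism is not, so asking more of route B is defensible. This stands as a reason to keep the broad cohort. It does not supply the self-harm component on route A, and it leaves the threshold dependent on local coding.

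**A reader might infer that the cohort is not the target group at all.** The documents do not support that. F60.3 entrants meet the BPD part, many may self-harm, and no share without self-harm is given. The cohort is simply not restricted to the target group.

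**A reader might infer that dilution leaves the study underpowered.** At the expected 200 per group, the power example survives unaffected shares up to 40%; it fails only at larger assumed shares such as 60%. The assumed halving may also already include dilution: the Lund figure under PRELIMINARY AND PREVIOUS RESULTS is for persons with BPD, with no self-harm requirement stated.

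**A reader might infer that F60.3 coding rises when BA arrives and creates a false benefit.** Nothing in the documents says so. METHODS reports differences between sites, not over time.

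**The plan has some protection.** The pairwise comparison before BA could reveal a stable baseline difference, and register data are requested so that confounders can be adjusted for or examined in subgroups. But entry route is not named, no covariate set or model is given for the site comparisons, and no difference-in-differences is specified that would remove a stable difference.

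**Conclusion.** The point holds in this form: the criteria admit people outside the stated target group, and the two thresholds tie severity at entry and the earliest qualifying date to coding habits that the plan itself says differ. No adjustment for diagnosis or route is listed for the comparisons that answer the primary question. A coding change over time would not cancel either, although none is documented.

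The size of any bias cannot be derived from the documents. The 6-point artefact, significant in about 23% of comparisons, rests wholly on the assumed shares and rates. It shows that a moderate difference in case mix can matter at the planned size, not that one exists. Power is not the main issue. What is at stake is bias in the site and before/after comparisons, and a conclusion worded for a population narrower than the one studied. This should be changed before analysis.

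**What to change.** 1. Keep the broad cohort. Stratify or adjust the primary before/after and site comparisons by entry route (F60.3 v two X60-83 admissions plus a listed diagnosis), with a stated rule for people who meet both.
2. Tabulate entrants by route, site and period, so that a site difference or a coding shift can be seen.
3. Prespecify a sensitivity analysis of the primary outcome in people with at least two X60-83 admissions whatever the diagnosis. Define it from history before BA began at the earlier site of each pair, using the same calendar window at both sites: from 2010 to the 2015 start in Lund for Lund and Linköping, and from 2010 to the 2017 start in Helsingborg for Helsingborg and Norrköping. Requiring a second self-harm admission after BA starts would select on an event that BA may prevent.
4. Describe the main population as people admitted with BPD, or with repeated self-harm plus a listed diagnosis. Reserve repeated self-harm for the restricted analysis. This wording follows from the criteria and should not depend on whether the two analyses agree.

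Cost: one covariate or stratification, one table and one extra analysis, from diagnoses and care dates already requested. The restricted set is smaller, omits people who enter after BA starts, and depends on how completely X60-83 is coded, so it stays a sensitivity analysis. Selecting on past admissions also makes a later fall likely at either site, so it is best read between sites. Adjusting for route does not remove severity differences within the F60.3 route; the restricted analysis addresses these only in part.

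### The two median-length outcomes count only admissions that still occur, so a change in them mixes stay length with which admissions and people remain

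*Combined protocol and SAP*

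**What the plan says.** The protocol section Outcome Measures and Comparisons gives the primary outcome as "Days with compulsory admission (days/year". The secondary list includes "Number of compulsory admissions (admissions/year" and two length measures: "Compulsory admission – median length (days/admission" and "Voluntary psychiatric admissions – median length (days/admission". Beyond the unit, neither length measure is defined. The plan does not say whether the median is over all admissions or over persons, what happens to someone with no admission in a period, or which direction is favourable.

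The Statistical Analyses Plan lists before/after comparisons within sites and pairwise comparisons between sites. It exempts no outcome from them. None of the seven research questions asks about length per admission.

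On mechanism, the Area Overview reports that about a fifth of hospital days in the earlier trial's BA group were BA, "implying that BA may partly substitute voluntary or compulsory admission to psychiatric care". It does not say whether the replaced stays were short or long.

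**The concern.** Length per admission exists only when there is an admission, and research question 2 asks whether BA reduces the number of compulsory admissions. The measure is therefore conditioned on something the intervention is meant to change. A person whose admissions all disappear, which is the best result, contributes nothing to the later median. This is so whether the median is pooled over admissions or first taken within persons. The before and after medians then describe different sets of stays and people. Adjusting for register covariates does not remove a selection that the intervention itself produces.

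At stake is the reading of two secondary outcomes. A rise could be reported as longer stays, a fall as shorter stays, or no change as no effect, when all that changed is which stays occurred.

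**Working it through.** **The plan's own figures.** The plan gives no figure for stay length. Its only calculation, 66 per group for 50% versus 25% with at least one admission over 7 days, reproduces with a two-sided 5% test, 80% power and a continuity correction (58 without the correction). It is unaffected by this point. It is used here only for its 7-day cut.

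**Arithmetic example (assumed lengths).** Ten stays of 2, 2, 3, 3, 4, 6, 10, 14, 21 and 35 days have median (4+6)/2 = 5 and total 100 days. Remove the four shortest. The rest (4, 6, 10, 14, 21, 35) have median (10+14)/2 = 12 and total 90 days. Days fall 10% and the median more than doubles, yet no stay lengthened.

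**General calculation.** Assumptions, because the documents give no length distribution: lognormal lengths with median m of 5–10 days and log-SD s of 1.0–1.3; short means 7 days or less; BA averts a fraction a of short stays and b of longer ones; remaining stays keep their length.

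- Share of stays that are short: F = Φ(ln(7/m)/s)
- Share of days in short stays: D = Φ(ln(7/m)/s − s)
- Admissions ratio: N = (1−a)F + (1−b)(1−F)
- Days ratio: (1−a)D + (1−b)(1−D)
- New median: m·exp(s·Φ⁻¹(q)), where q = N/(2(1−a)) if (1−a)F ≥ N/2, otherwise q = 1 − N/(2(1−b))

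**Worked case, m = 7, s = 1.0.** F = 0.5 and D = Φ(−1) = 0.1587.

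- a = 0.5, b = 0: N = 0.75; days ratio 1 − 0.5×0.1587 = 0.921; q = 1 − 0.75/2 = 0.625; median 7·exp(0.319) = 9.6.
- a = 0.7, b = 0.4: N = 0.45; days ratio 0.3×0.1587 + 0.6×0.8413 = 0.552; q = 1 − 0.45/1.2 = 0.625; median 9.6 again.
- a = b = 0.5: N = 0.50; days ratio 0.50; q = 0.5; median 7.0.
- a = 0.3, b = 0.6: N = 0.55; days ratio 0.7×0.1587 + 0.4×0.8413 = 0.448; q = 0.55/1.4 = 0.393; median 7·exp(−0.272) = 5.3.

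The first two cases give the same median because only the ratio (1−a)/(1−b) matters for it, and that ratio is 0.5 in both. Total days depend on a and b separately. That is why the median does not track the primary outcome.

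**Across the assumed range (m 5–10, s 1.0–1.3):**

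| Short averted | Longer averted | Change in days | Change in median |
|---|---|---|---|
| 50% | 0% | −3% to −13% | +26% to +65% |
| 70% | 40% | −42% to −48% | +26% to +65% |
| 50% | 50% | −50% | none |
| 30% | 60% | −52% to −58% | −18% to −35% |

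The extremes of the rise are m = 10, s = 1.0 (10 to 12.56 days, +26%) and m = 5, s = 1.3 (5 to 8.27 days, +65%). The second and third rows are close to or equal to the halving of compulsory days that the Statistical Analyses Plan treats as reasonable.

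**The case against.** The strongest objection is that nothing shows BA averts mainly short stays. A BA stay is short ("With admissions limited to a maximum of three nights, three times per month"), but that does not fix the length of the stay it replaces. Some of the text leans the other way. The Area Overview names "aggravated self-harm and prolonged compulsory admissions" as iatrogenic effects of inpatient care. The power example is built on fewer people having an admission over 7 days. If long stays are averted more, the median falls along with compulsory days.

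This stands, and it rules out a stronger reading that a reader might infer: that a working BA would make compulsory stays look longer, so that the outcome points the wrong way. That holds only if short stays are averted at a higher rate. The plan also states no favourable direction. The nearest hint is in Preliminary and Previous Results, where "only the BA group showed a significant decrease in duration of compulsory admissions and frequency of NSSI" is offered as encouraging. The Area Overview describes the same trial's finding as fewer days with compulsory admission, so it need not concern length per stay.

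The objection does not rescue the measure. A fall produced by averting long stays would still be misread as stays becoming shorter.

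Two further objections also hold in part. Days/year and admissions/year are listed for both admission types, so a careful reader could detect a change in mix. It might also be inferred that a few frequently admitted people dominate the figure. That assumes pooling over admissions, which the unit alone does not settle.

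**Conclusion.** The point holds. A difference in either median cannot be attributed to stay length, because the set of stays being compared may itself change with BA. The three directions follow from arithmetic. The sizes rest on the assumed lognormal lengths, the 7-day cut and the chosen averting fractions. Over a wider assumed range (medians of 4, 7 and 14 days, log-SD 0.8–1.6), averting 70% of short and 40% of longer stays still raised the median in every setting, with days down 41%–54%. Averting 30% and 60% lowered it in every setting, with days down 46%–59%.

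The documents do not support predicting which of these will occur. Severity is modest: both outcomes are secondary, the information needed to interpret them is already listed, and the primary outcome and the sample size are untouched. It is a cheap improvement that changes what may be concluded about stay length.

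**What to change.** In Outcome Measures and Comparisons, mark both medians as descriptive, with no test and no claim of effect. State whether they are taken over admissions or persons, and that people without an admission do not contribute. State that they are read only together with admissions/year and days/year.

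For any claim about stay length, use rates with the whole cohort in the denominator, including people with zero admissions. One choice is admissions per person-year of more than 7 days and of 7 days or less, for compulsory and for non-BA voluntary admissions. The 7-day cut is already in the plan's power example, so no new threshold is needed. These rates do not separate an averted long stay from a shortened one, but averted stays remain visible as a lower rate.

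Cost: wording only, using the admission and discharge dates that days/year already requires. The downside is two rates in place of one number for each admission type, with slightly more multiplicity among the secondary outcomes.
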